### **8.2.2. Methods and timeframes for assessment and documenting of safety variables**

The safety analysis will include all patients who received at least one dose of the investigational product. Additionally, the SAE analysis will include all randomized patients starting from the ICF signing and until the end of their participation in the study.

Safety will be analyzed based on the information about

- AEs/SAEs,
- Physical examination data and vital signs,
- CBC, blood chemistry, and urinalysis results,
- ECG findings.

The frequency of these procedures is specified in section 4.6.1 “Schedule of study visits and procedures”. AEs/SAEs will be documented and reported in accordance with the Sponsor’s Manual.

The investigator is responsible for recording adverse events in the clinical study.

AEs are recorded beginning from the moment when the investigational product was injected the first time until the end of the follow-up period after the patient stopped taking the investigational product (as planned or prematurely). SAEs are recorded from the moment when the subject signed the informed consent form until the moment when he/she completed the study (as planned or prematurely). SAEs that were recorded during screening are not included in the total safety analysis. The Investigator can record an SAE later than stipulated by the Protocol if he/she believes that this SAE is related to the investigational product or study procedures.

An AE is considered to be resolved if the laboratory parameter, vital sign or symptom has returned to its baseline value. For all parameters, the baseline level is considered the value/sign severity that was seen in this patient before the first injection of BCD-085/placebo at the first scheduled visit per protocol. For AEs, including SAEs, of long-lasting/chronic nature, the resolution is the stabilization of the patient’s condition. For example, the AE “aggravation of chronic bronchitis” is considered to be resolved when the patient has achieved remission.

The Investigator must document non-serious AEs in the source documents and in the CRF, and show them to the Monitor at the next monitoring visit. Besides being recorded in the source documents and eCRF, serious adverse events (SAEs) must be reported to the Sponsor within 24 h in the SAE Report Form. SAE Report Forms must be sent to the Sponsor within 24 h by email to

## **8.3 Requirements for reports, procedures for registration and reporting AEs, and filling out AE Report Forms**

### **8.3.1. Recording AEs/SAEs**

At every visit, a record should be made whether or not any AE occurred during the period from the previous visit. Any adverse event reported for a patient since he/she signed an informed consent form had to be recorded in source documents and in a special form for registration of adverse events (attachment to the CRF). AEs will be documented in accordance with the Sponsor's Manual.

AEs are recorded and numbered consecutively as they occur. Each AE is reported in an *AE Report Form*. Rules for documenting AE/SAE are described in detail in the Sponsor's Manual.

Adverse events must be recorded regardless of their seriousness and causal relationship with the study therapy. If an adverse event re-emerges, it should be recorded as a new AE and assigned a new number.

#### **Laboratory and vital sign abnormalities**

Laboratory and/or vital sign abnormalities considered to be adverse events (assessed as clinically meaningful, including those of CTCAE 4.03 grade 1, inducing clinical symptoms or complaints requiring concomitant therapy or changes in study therapy) must be recorded in the CRF, *Adverse Events* section. CTCAE 4.03 grade 1 adverse events are registered only if the investigator considers the event clinically meaningful. Starting from CTCAE 4.03 grade 2, all adverse events should be recorded, regardless of their clinical significance. It is preferable to specify diagnosis rather than individual symptoms (for example, anemia instead of reduced hemoglobin). Laboratory abnormalities meeting the criteria for an adverse event should be followed up until they return to normal or until an adequate explanation is obtained.

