At least one AE/SAE was reported in 45.16% (14 of 31) of patients in Arm 1, 36.67% (11 or 30) of patients in Arm 2, 25.00% (7 of 28) of patients in Arm 3, and 39.29% (11 of 28) of patients in Arm 4 ( $P = 0.443$ , two-sided  $\chi^2$  test with Yates correction). AEs/SAEs were judged as related to the study treatment in 6 (19.35%) patients in Arm 1, in 3 (10.00%) patients in Arm 2, in

Translated from Russian to English, dated 26-Nov-2019

2 (7.14%) patients in Arm 3, and in 3 (10.71%) patients in Arm 4 ( $p=0.534$ , two-sided Fisher's exact test). The pairwise comparison of the overall frequency of AEs/SAEs and the frequency of treatment-related AEs/SAEs did not reveal any significant differences between the study arms ( $P > 0.05$ ).

**Table 13.** Assessment of safety in the Phase II study (Arm 1: BCD-085 40 mg, Arm 2: BCD-085 80 mg, Arm 3: BCD-085 120 mg, Arm 4: placebo).

Abnormality	Arm			
	1 (n = 31)	2 (n = 30)	3 (n = 28)	4 (n = 28)
Any AEs/SAEs	14 (45.16%)	11 (36.67%)	7 (25.00%)	11 (39.29%)
P value 	0.443			
Treatment-related AEs/SAEs	6 (19.35%)	3 (10.00%)	2 (7.14%)	3 (10.71%)
P value 	0.534			
AEs, Grade 3	1 (3.23%)	1 (3.33%)	1 (3.47%)	2 (7.14%)
P value 	0.872			
Treatment-related AEs, grade 3	1 (3.23%)	1 (3.33%)	0	0
P value 	1.000			
Injection site reactions	1 (3.23%)	0	0	0
P value 	1.000			
Treatment discontinuation due to AEs/SAEs	None			
Any SAEs				
AEs, grade 4				

Note:  two-sided Fisher's exact test;  Pierson's  $\chi^2$  test with Yates correction.

In this study, no grade 4 AEs and no SAEs were recorded. No patients had to discontinue the study treatment due to AEs/SAEs.

The most common AEs were neutropenia, acute respiratory tract infections, increased blood pressure, and elevated liver transaminases. Most of the AEs were mild in severity. Grade 3 AEs were reported in 3.23% of patients in Arm 1, 3.33% of patients in Arm 2, 3.57% patients in Arm 3, and 7.14% patients in Arm 4 ( $p=0.872$ , two-sided Fisher's exact test).

Only one injection site reaction (grade 1) was detected in Arm 1 manifesting as swelling in the injection site. The investigator did not consider this event clinically meaningful. The

BCD-085 40 mg, 80 mg, and 120 mg demonstrated a favorable safety profile. The nature and severity of adverse events seen in three BCD-085 arms did not significantly differ from that in the placebo arm.

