## **8. ASSESSMENT OF SAFETY**

### **8.1. List of safety variables**

#### **8.1.1. Terms and definitions**

##### **8.1.1.1. Adverse events**

Adverse Event (AE) is any untoward medical occurrence in a patient or clinical investigation subject administered a pharmaceutical product and which does not necessarily have to have a causal relationship with this treatment.

An AE can, therefore, be any unfavorable and unintended sign (including an abnormal laboratory finding), symptom, or disease temporally associated with the use of a medicinal product, whether or not related to the medicinal product: from the first dose of the investigational product and until the end of the protocol-specified follow-up period.

Negative medical events that occurred before the administration of the investigational product (including those found at Visit 1 but before the administration of the investigational product) are not considered to be adverse events. These conditions are background for this patient.

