### **8.1.2. Safety endpoints**

- Proportion of patients who developed AEs/SAEs.
- Proportion of patients who developed injection site reactions.
- Proportion of patients who developed Grade 3/4 AEs/SAEs.
- Proportion of patients who discontinued the study due to AEs and/or SAEs.
- Exposure adjusted incidence rate of AEs/SAEs during the extension study.

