#### **Special rules for AE registration**

- Aggravation or worsening of the main disease or any symptoms of the main disease are not reportable as AEs **even if they have any seriousness criteria**. The event should not be documented as an SAE if hospitalization is the only seriousness

criterion, while the AE is represented by worsened signs or aggravation of the main disease.

- If the patient had no clinical/laboratory abnormalities at baseline, any grade 2 or higher (grade 1 or higher if the investigator considers it clinically meaningful) clinical/laboratory abnormality must be documented as an AE. If the patient had clinical/laboratory or other abnormalities at baseline, any increase in severity of this abnormality or any other worsening judged by the Investigator as clinically meaningful must be reported as an AE.
- The event should not be documented as an SAE if hospitalization is the only seriousness criterion, while the AE is represented by worsened signs or aggravation of the main disease.
- Cases of confirmed positive results of Diaskintest, QuantiFERON or T-spot are recorded as adverse events.

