### **Injection site reactions**

In this clinical study, investigators will evaluate injection site reactions after the administration of BCD-085/placebo. Assessments will be performed on the same visits when injections will be given. Assessment includes visual examination of the injection site (and sites where injections were given in the past if this is not the first visit) and collection of patient's complaints. The Injection Site Reaction Form is presented in Annex 1. The Injection Site Reaction Report Form should be filled out only if an injection site reaction is recorded (starting from grade 1). If there are no injection site reactions, this form is not filled out. Injection site reactions of grade 2 or higher must be registered as adverse reactions. If the investigator considers a grade 1 injection site reaction to be clinically meaningful, it also must be registered as an adverse event. Severity grades for injection site reactions are presented in Annex 1.

**Among other laboratory/vital sign/clinical abnormalities not found at Visit 1 before the first injection of the investigational product, the following is recorded:**

- All abnormalities of CTCAE 4.03 grade 2 and higher.
- Grade 1 abnormalities should be recorded as AEs only if clinically relevant, i.e. if the Investigator considers the abnormality to be substantial with account of the main and concurrent illnesses. Single abnormalities found among multiple laboratory test results or

---

 If retest is performed, its results are considered.

incidental low values should not be reported as AEs, except for events that are clinically relevant.

If revealed during the period between scheduled visits (for example, when the patient comes to the study site for dialysis), a laboratory/vital sign/instrumental abnormality can be recorded by the Investigator in the eCRF if clinically meaningful (regardless of its severity grade). The Investigator specifies the onset date, the fact that the AE occurred between visits, and the reason why the AE was recorded (for example, numerical values of laboratory and/or vital signs).

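### Registering grade 1 events as AEs only when the investigator finds them meaningful conflicts with the protocol's own AE definition and recording rule, so the any-AE proportion can miss mild clinical events

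*Protocol*

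**What the plan says.** **Rules without a threshold.** Protocol 8.1.1.1 counts as an AE "any unfavorable and unintended sign (including an abnormal laboratory finding), symptom, or disease temporally associated with the use of a medicinal product". Protocol 8.3.1 opens with a recording rule: "Any adverse event reported for a patient since he/she signed an informed consent form had to be recorded in source documents" and on the AE form. Neither mentions grade.

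**Rules with a threshold.** Three later parts of 8.3.1 add one.

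- Under *Laboratory and vital sign abnormalities*: "CTCAE 4.03 grade 1 adverse events are registered only if the investigator considers the event clinically meaningful". The next sentence removes discretion above that level: "Starting from CTCAE 4.03 grade 2, all adverse events should be recorded, regardless of their clinical significance".
- Under *Special rules for AE registration*, where the baseline was free of such findings: "any grade 2 or higher (grade 1 or higher if the investigator considers it clinically meaningful) clinical/laboratory abnormality must be documented as an AE".
- In the list after the injection site reaction text, which covers laboratory, vital-sign and clinical findings not present at Visit 1: "Grade 1 abnormalities should be recorded as AEs only if clinically relevant".

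**Endpoints that use the record.** Protocol 8.1.2 and SAP 4.2 list five safety endpoints. They include the share of patients with any AE or SAE, the extension exposure-adjusted rate, and "Proportion of patients who developed Grade 3/4 AEs/SAEs". Objective 3 (Protocol 2.2, SAP 2.2) asks for the AE proportion by arm and a safety comparison of Q4W with Q2W. The SAP does not split AEs into all grades and grade 2 or higher, and its section 9 plans no additional analyses.

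**The concern.** Read alone, the first filter could pass as a rule about laboratory noise, because its heading limits it to laboratory and vital-sign values. The two later passages name clinical abnormalities as well. A mild infection or headache is thus an AE under the definition and the opening rule, and may be omitted under the later text. Sites that follow different paragraphs would record the same event differently, and a reader of the AE table would not know that it is filtered.

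Mild events matter here. Protocol 1.4.2 names infection as an anticipated risk of blocking IL-17, and the summary of the ankylosing spondylitis extension study treats Candida infections as events of special interest for the class. On the earlier psoriasis study the protocol reports: "Most of the AEs were mild in severity". If mild clinical events drop out, the any-AE proportion is too low in every arm, and a true difference in mild events between regimens becomes harder to see.

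**Working it through.** **1. The passages side by side**

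| Place | Grade threshold | Covers clinical events |
|---|---|---|
| Protocol 8.1.1.1, definition | none | yes |
| Protocol 8.3.1, opening rule | none | yes |
| 8.3.1, laboratory and vital signs | grade 1 filtered | heading says no, sentence speaks of adverse events |
| 8.3.1, special rules | grade 1 filtered | yes, named |
| 8.3.1, list after injection site reactions | grade 1 filtered | yes, named |

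One sentence of the opening subsection forbids selection by seriousness or causality. It does not mention grade, so the conflict is with the definition and with the rule that any reported AE is recorded.

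**2. Where discretion remains above grade 1.** For a patient with a baseline abnormality, the special rules leave other worsening to the investigator's view of clinical meaning, with no grade limit. The last paragraph of the injection site reaction text does the same for findings made between scheduled visits. Grade 2 or higher is therefore largely, not wholly, free of discretion.

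**3. Who knows the arm, and when.** Protocol 4.3.5 keeps investigators and patients blinded until Week 12 and unblinds from then. The Q2W and Q4W schedules differ only through Week 10. From Week 14, Arms 1 and 2 are both on Q4W, and Arm 3 starts BCD-085 at Week 12. The SAP's final report (section 5) covers Weeks 0 to 12. Protocol 8.2.1 places safety analyses at Weeks 12 and 54.

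**4. Illustration of size.** The plan gives no figure to reproduce. Let p be the true proportion of patients with any AE, g the share of these whose events are all grade 1, and r the share of those patients who are registered. All three are assumptions.

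Recorded proportion = p × (1 − g + g × r)

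The earlier psoriasis studies help to place p, although the documents do not give their registration rule: 7/28 = 25.0% (120 mg), 11/28 = 39.3% (placebo), 38/103 = 36.9% (extension). The grade-1-only share is not reported.

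- p = 0.40, g = 0.50: 0.40 × 0.50 = 20% at r = 0; 0.40 × 0.75 = 30% at r = 0.5; 40% at r = 1.
- Floor at r = 0 over p = 0.25 to 0.55 and g = 0.30 to 0.80: from 0.25 × 0.20 = 5% to 0.55 × 0.70 = 38.5%.

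**5. Effect on a comparison.** If g and r are the same in both arms, the recorded difference is the true difference × [1 − g(1 − r)].

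- g = 0.4, r = 0.7: 1 − 0.4 × 0.3 = 0.88, so 10 points appear as 8.8.
- g = 0.7, r = 0.3: 1 − 0.7 × 0.7 = 0.51, so 10 points appear as 5.1.
- With p and g equal in both arms, there is no false difference in expectation: 30% v 30% at r = 0.5 above.

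A false difference needs r to differ by arm. With p = 0.40, g = 0.50 and r = 0.75 v 0.25, the recorded figures are 35% v 25%. At 85 per arm the pooled standard error is √(2 × 0.30 × 0.70/85) = 0.0703 and the unpooled one is 0.0699. The chance of nominal p < 0.05 is about Φ[(0.10 − 1.96 × 0.0703)/0.0699] = Φ(−0.54), or 29%. That contrast in r is deliberately large, and nothing in the documents suggests it.

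**The case against.** The strongest reply is that a prespecified grade 1 threshold, applied alike to all arms, is a legitimate design choice and that little is lost. Much of this stands. Events from grade 2 are recorded as a rule, and serious events are recorded. Injection site reactions go on their own form from grade 1 and have their own endpoint. Laboratory values and vital signs are analysed directly. The extension diary captures health information as a source document. The Sponsor's Manual, which 8.3.1 cites for detailed rules, is not among the documents and may say more.

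Three stronger readings are tempting, and the documents do not support them.

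- *That the trial's main safety endpoint rests on discretion.* No document ranks the five safety endpoints; the any-AE proportion is only listed first. Only patients with grade 1 events alone depend mainly on the filter.
- *That open-label judgement biases the Q4W v Q2W comparison.* The regimens differ only while treatment is blinded, and the two arms then share one regimen. No reason appears why registration would differ between them.
- *That earlier studies show the filtered class to be large.* All five non-serious Phase I events were grade 1, but they were ALT, AST and neutrophil findings. Three of the four most common AE types in the Phase II psoriasis study were laboratory or vital-sign events. The fix would leave isolated grade 1 values of this kind filtered. No figure is given for grade 1 clinical events.

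What the reply does not remove is the conflict itself. A deliberate threshold would have to be stated in the definition and in the endpoint label, and it is in neither.

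**Conclusion.** The conflict holds on the text alone. The definition and the opening recording rule set no threshold; three later passages filter grade 1 events, and two of them name clinical abnormalities. The any-AE proportion and the extension exposure-adjusted rate can therefore miss mild clinical events.

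Up to Week 12 the expected consequence is under-counting and, if the grade-1-only share and the registration rate are similar across arms, a smaller apparent difference. Judgement with the arm known is confined to the Week 54 and extension results. The magnitude cannot be derived from the documents: the 20% to 40% range and the factors of 0.51 to 0.88 are illustrations on assumed inputs.

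A smaller wording gap sits at the other end of the scale. Read literally, the severe-event endpoint stops at grade 4, and the protocol's summary of the ankylosing spondylitis extension study lists deaths apart from grade 4 events. A reader might infer that a death would go uncounted. It would not: death is a seriousness criterion in 8.1.1.2, so a fatal event is an SAE and enters the any-AE endpoint.

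**What to change.** 1. **Protocol 8.3.1.** Limit the clinically meaningful filter to isolated grade 1 laboratory and vital-sign values in all three places, and record every clinical AE of any grade. Bring the paragraph on findings between visits into line. If the sponsor prefers to keep the wider filter, the definition and the endpoint label should say so.
2. **SAP 4.2 and 8.2.** Tabulate the AE proportion for all grades and, separately, for grade 2 or higher. Describe the second row as largely, not wholly, free of investigator discretion.
3. **Protocol 8.1.2 and SAP 4.2.** Word the severe-event endpoint as grade 3 or higher, so that a fatal event is in that count too.

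The cost is protocol and SAP wording, more mild-event entries in the eCRF, and one extra row in the AE table.

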#### **Special rules for AE registration**

- Aggravation or worsening of the main disease or any symptoms of the main disease are not reportable as AEs **even if they have any seriousness criteria**. The event should not be documented as an SAE if hospitalization is the only seriousness

criterion, while the AE is represented by worsened signs or aggravation of the main disease.

- If the patient had no clinical/laboratory abnormalities at baseline, any grade 2 or higher (grade 1 or higher if the investigator considers it clinically meaningful) clinical/laboratory abnormality must be documented as an AE. If the patient had clinical/laboratory or other abnormalities at baseline, any increase in severity of this abnormality or any other worsening judged by the Investigator as clinically meaningful must be reported as an AE.
- The event should not be documented as an SAE if hospitalization is the only seriousness criterion, while the AE is represented by worsened signs or aggravation of the main disease.
- Cases of confirmed positive results of Diaskintest, QuantiFERON or T-spot are recorded as adverse events.

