##### **8.1.1.2. Serious adverse events**

A Serious Adverse Event (SAE) is any untoward medical occurrence that at any dose:

- Results in death;
- Is life-threatening;
- Requires hospitalization or prolongation of existing hospitalization;
- Results in persistent or significant incapacitation or disability;
- Is a congenital anomaly or birth defect.

In case of any uncertainty whether the event meets the seriousness criteria or not, it should be treated as a serious adverse event.

Immediate risk of death from a reported event is considered **life-threatening**. A life-threatening event does not include an adverse event that, had it occurred in a more severe form, might have caused death, but is not associated with an immediate risk of death in the form it occurred. For example, hepatitis that resolved without any signs of hepatic insufficiency will not be considered life-threatening, although more severe hepatitis can lead to fatal outcome. Similarly,

Translated from Russian to English, dated 26-Nov-2019  
an allergic reaction resulting in face angioedema will not be considered life-threatening despite the fact that larynx angioedema, allergic bronchospasm or anaphylaxis may lead to a fatal outcome.

**Hospitalization** is an official admission to the hospital. Hospitalization or its prolongation is a criterion of AE seriousness; however, hospitalization itself is not a serious adverse event. Hospitalization or its prolongation not associated with AE should not be reported by the Investigator as a serious adverse event. This is applicable (including but not limited) to the following cases:

- Hospitalization or prolongation of existing hospitalization is necessary to perform procedures required by the Protocol.
- Hospitalization or prolongation of existing hospitalization is a part of routine procedures in this study site (for example, stent removal after a surgery). An appropriate confirmation should be kept in the study file.
- Hospitalization because of a previous condition (recorded before the patient signed the ICF), for example, hospitalization for kidney transplantation because a donor organ has become available, surgery for cataract diagnosed before the patient signed the ICF, etc.

**Disability** is defined as a significant or persistent loss of the ability to work because of a disease, injury, their consequences or other reasons during a definite period (temporary disability) or a long indefinite period.

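### Protocol 8.3.1 gives two conflicting rules on serious worsening of psoriasis, and the broader one contradicts the SAE definition in 8.1.1.2

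*Protocol*

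**What the plan says.** The special rules for AE registration in Protocol 8.3.1 contain three statements that bear on worsening psoriasis.

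- The first bullet opens with a blanket exemption: "Aggravation or worsening of the main disease or any symptoms of the main disease are not reportable as AEs". An emphasised rider extends it: "even if they have any seriousness criteria".
- The same bullet continues: "The event should not be documented as an SAE if hospitalization is the only seriousness criterion". The rest of that sentence limits it to worsening of the main disease. The whole sentence appears again as a bullet of its own.
- Between the two, a bullet on patients with abnormalities at baseline says that "any increase in severity of this abnormality or any other worsening judged by the Investigator as clinically meaningful must be reported as an AE". It makes no exception for psoriasis.

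Earlier in 8.3.1 the general rule is "Adverse events must be recorded regardless of their seriousness and causal relationship with the study therapy".

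Section 8.1.1.2 starts its definition with "A Serious Adverse Event (SAE) is any untoward medical occurrence that at any dose" and lists the criteria, beginning with "Results in death" and going on to life-threatening events, hospitalization and disability. Its stated exceptions concern hospitalization, for example admission for a condition recorded before consent. None concerns the main disease as such.

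**The concern.** A site has to decide what to do with a psoriasis flare that is life-threatening, disabling or fatal. The emphasised sentence says it is not an AE. The sentence after it makes sense only if such a flare can be an SAE.

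The choice decides whether the event is reported. Under 8.3.2 the SAE form is completed when the investigator considers an AE to be an SAE, and under 8.2.2 that form carries the 24-hour report. Section 8.2.1 has the sponsor's drug safety division review each SAE once its report arrives. An event denied AE status enters none of these steps. It also drops out of the safety endpoints in Protocol 8.1.2 and SAP 4.2, which count AEs/SAEs, Grade 3/4 AEs/SAEs and discontinuations due to them. Protocol 9.5 sets no statistical stopping criteria, so oversight of serious events rests largely on individual reports.

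**Working it through.** No figure in the plan depends on this wording, so there is nothing to recompute. The check is to apply each rule to the same events.

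| Psoriasis worsening that… | First sentence of the bullet | Hospitalization-only sentence | Definition in 8.1.1.2 |
|---|---|---|---|
| meets hospitalization alone | not an AE, so not an SAE | not an SAE | meets a listed criterion, subject to the section's hospitalization exceptions |
| is life-threatening | not an AE, so not an SAE | SAE by implication | SAE |
| is disabling | not an AE, so not an SAE | SAE by implication | SAE |
| is fatal | not an AE, so not an SAE | SAE by implication | SAE |

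1. The first two columns agree in the top row and differ in the other three. If the first sentence governs, the word *only* in the second has no function, because no worsening could be an SAE on any criterion.

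2. The second sentence, in both places, also calls the worsening an AE. The first sentence denies it that status.

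3. In the three disputed rows the definition in 8.1.1.2 agrees with the implied reading of the second sentence and contradicts the first. The exceptions in 8.1.1.2 are also about hospitalization, which fits a hospitalization-only exemption and not a blanket one.

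4. The bullet on baseline abnormalities points the same way. Every enrolled patient has psoriasis at baseline, and that bullet requires clinically meaningful worsening to be reported without excluding it.

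5. Other routes to the sponsor:
   - **Death** is a withdrawal criterion in 4.8.2, and the sponsor must be told of a withdrawal, with the reason, within 24 hours.
   - **Need for prohibited treatment**, which includes systemic psoriasis therapy and phototherapy, requires withdrawal under 6.2.2. The same notice follows.
   - **Serious worsening without withdrawal** has no equivalent. PASI and sPGA at scheduled visits record skin severity, not whether an event was serious.

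   The first two routes inform the sponsor, but they are withdrawal notices. They do not create an SAE report or enter the event in the AE/SAE endpoints.

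**The case against.** The strongest reply is that the conflict arises by implication. The second sentence never says that worsening meeting another criterion is reportable. Read strictly, the two sentences are compatible: if no worsening is an AE, hospitalization-only worsening is not an SAE either, and the repeated bullet may be an editing remnant in a translated text. This stands as a limit on how the point may be put. It does not remove the problem, because that reading empties the second sentence of content and still leaves the first in conflict with 8.1.1.2.

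Sections 8.2.2 and 8.3.1 refer sites to the Sponsor's Manual for the detailed rules. The Manual may settle the matter. It was not supplied, and the protocol text would still need to agree with it.

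A reader might go further in four ways that the documents do not support.

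- **That a fatal flare would be hidden from the sponsor.** The withdrawal notice should reveal it. What is lost is its status as an SAE.
- **That 8.1.1.2 settles the case through its rule on doubt.** That rule reads "In case of any uncertainty whether the event meets the seriousness criteria or not, it should be treated as a serious adverse event". It covers doubt about the seriousness criteria. With a fatal flare, seriousness is clear; the doubt is whether the main-disease exemption applies.
- **That the arms will be unevenly affected, with more events lost on placebo before Week 12.** This is plausible, since 1.5.3 anticipates that a patient's disease may worsen and that the patient may then leave. But no rate of serious worsening is given. The Phase II psoriasis study described in the protocol recorded no SAEs among 117 patients, 28 of them on placebo, and its reporting rule is not stated. One event among 43 placebo patients is 1/43 = 2.3 percentage points, but that holds for any event and does not measure the effect of this rule.
- **That worsening goes uncollected.** PASI and sPGA are recorded in all arms at screening and at Weeks 8 and 12, so ordinary worsening of the skin can be tabulated.

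**Conclusion.** The point holds as an internal inconsistency in a safety-reporting rule. Protocol 8.3.1 contains a blanket exemption and a hospitalization-only exemption, the blanket one contradicts 8.1.1.2, and no supplied text ranks them. A site that follows the first sentence may keep life-threatening, disabling or fatal worsening off the SAE form and out of the AE/SAE endpoints. The clearest gap is serious worsening that does not lead to withdrawal.

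The size cannot be stated. The documents give no frequency for such events and no basis for a difference between arms, and the number is probably small. It is also not established that sites will in fact diverge, since the Manual may direct them to one reading. Exempting main-disease worsening from AE reporting is not in itself shown to be wrong; the fault is that the exemption's extent is stated in two ways. The correction is still worthwhile because it is cheap and concerns the most serious events.

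**What to change.** Reconcile the sentences in 8.3.1 with each other and with 8.1.1.2, so that one reporting rule applies and the exemption for serious worsening does not extend beyond hospitalization-only cases.

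- Delete the rider "even if they have any seriousness criteria" and the duplicate bullet.
- State expressly that worsening of psoriasis meeting any criterion other than hospitalization is recorded as an AE and reported as an SAE. Deleting the rider alone is not enough, because the remaining sentence would still deny all worsening AE status.
- Say whether the bullet on worsening of baseline abnormalities applies to psoriasis.
- Check that the Sponsor's Manual says the same.

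A separate eCRF line for exempted worsening is optional. It would help mainly with events between scheduled PASI and sPGA assessments.

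The cost is a protocol wording change and a few more SAE reports. Sample size, endpoints and efficacy analyses are unaffected.
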